**6.2. Visit 2 (Baseline Day -4 up to -1 prior to dosing on Day 1)**

This visit *may* be conducted over 1 or 2 days as determined by the site.

**Clinical laboratory testing:**

- **Fasting blood collection:** serum ferritin, serum iron, TIBC and % transferrin saturation
- **Fasting blood collection** for Biomarker: Group 2.
- **Blood sample** for hormones (LH, FSH, T4, TSH, androstenedione, testosterone). Blood collection for hormones should be done in the morning.
- **Blood sample** for Biomarker: Liver.
- **Blood sample** for hematology, blood chemistry, GGT, GLDH, PT, aPTT, creatine kinase, amylase, cardiac troponin I and hormones (LH, FSH, T4, TSH)

androstenedione, testosterone). Blood collection for hormones should be done in the morning.

- **Blood sample** for immunogenicity.
- **Urine sample** for urinalysis.
- **Weight:** The subject's weight is required when randomizing the subject.
- **Height:** Height should be measured in the morning.
- **Functional Assessments** should be assessed in the morning: Must be conducted in the following order: FVC, 4SC, NSAA, ROM, strength assessment, PUL, 6MWT. Note: The time to complete the 4SC at baseline is required to stratify subjects at the time of randomization, however it is the 4SC at screening which will qualify them for the study.
- **Fecal occult blood:** Fecal sample is to be collected at home within approximately 1 week prior to scheduled visit.
- **Physical Examination:** including nose and throat mucosal exam.
- **Tanner Stage** and **testicular volume**.
- **Vital signs:** Supine blood pressure, pulse rate, respiratory rate, and oral temperature.
- **Triplicate ECG.**
- **PODCI** questionnaire.
- **C-SSRS:** Children's Since Last Visit (Version 6/23/10). This evaluation is required at baseline to confirm subject's eligibility.
- **Inclusion/Exclusion Criteria:** Subject eligibility will be confirmed against inclusion and exclusion criteria.
- **Randomization:** Randomization will occur after all screening evaluations are complete. Subject's eligibility is based on the screening assessments and the baseline C-SSRS. At the time of randomization, the baseline 4SC and weight are required to be entered into the IRT system. Subjects may be randomized once these assessments are complete and subject if determined to be eligible.

### 6.3. Visit 3 (Day 1)

#### **Prior to dosing, the following procedures will be completed:**

- **Blood samples** for PK.

- **Blood samples** for PD.
- **Vital signs:** Supine blood pressure, pulse rate, respiratory rate, and oral temperature.

**Dosing:**

- **Investigational product administration.**

**After dosing, the following procedures will be completed:**

- **Vital signs:** Supine blood pressure, pulse rate, respiratory rate, and oral temperature.

**Blood samples for:**

- **PK:** Collected following the completion of infusion and flush (hour 2).
- **PD:** Collected following the completion of infusion and flush (hour 2).
- **Infusion site reaction monitoring.**
- **Adverse event (AE) monitoring.**
- **Concomitant medication monitoring.**
- **Wellness phone check:** Approximately 1 week following each dosing visit, the site will call caregiver to verify if there are any AEs that have emerged since dosing.

**6.4. Visit 4, 8, 10, 14, 16, 20 (Day 8, 92, 120, 204, 232, 316) Additional PK visits**

The first 12 subjects enrolled in the study will be required to complete 6 additional visits to further characterize the PK profile of the study drug. Subjects enrolled after the first 12 subjects will not be required to complete these additional visits.

**Clinical Laboratory testing:**

- **Blood samples** for hematology, chemistry, GGT, GLDH, PT, aPTT, creatine kinase and amylase.
- **Blood sample** for Biomarker: Liver.
- **Blood sample** for PK.
- **Urine sample** for urinalysis.
- **Infusion site reaction monitoring.**
- **AE monitoring.**

- **Concomitant medication monitoring.**

**6.5. Visits 5, 11, 17, 22, 26, 30 (Days 29, 141, 253, 365, 477, 589)**

- **Fecal occult blood:** Fecal sample is to be collected at home within approximately 1 week prior to scheduled visit.
- **C-SSRS:** Children's Since Last Visit (Version 6/23/10).

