**Table 4. Period 2 Dosing Schedule**

Dosing Week	49	53	57	61	65	69	73	77	81	85	89	93
Sequence 1 PF-06252616 Dose	40 mg/kg (or maximum tolerated dose per each subject) once every 4 weeks											
Sequence 2 Placebo Dose	0 mg/kg once every 4 weeks											
Sequence 3 PF-06252616 Dose	5 mg/kg once every 4 weeks			20 mg/kg once every 4 weeks			40 mg/kg once every 4 weeks					

Note: Sequence 1 in this example shows all subjects tolerating the maximum dose level.

Following demonstration of tolerance at a lower dose, if subjects are unable to tolerate higher doses, their dose level may be reduced by a level at the time of dose escalation. Subjects in Sequence 1 will be treated at their maximum tolerated dose level from Period 1 when they enter Period 2 and they will not be escalated to additional higher doses during Period 2. Subjects in Sequence 3 will receive active drug in Period 2 in accordance with the dose adjustment criteria.

Subjects should be administered the investigational product within the visit window according to the schedule of activities. If a dosing visit cannot be conducted within the visit window, attempts should be made to bring the subject back for dosing as soon as possible; however the dosing must not occur within 2 weeks prior to the next scheduled dose. If the subject cannot return for dosing in this timeframe, the dose should be missed and the next visit should be conducted per the [Schedule of Activities](#).

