## 6. STUDY PROCEDURES

Every attempt should be made to schedule the visits on the day specified in the [Schedule of Activities](#). In order to provide optimal testing conditions and consistency in endpoint measurements, at visits when the functional assessments, imaging and clinical laboratory assessments are scheduled to be completed at the same visit, the visit should be completed on two days within the visit window and at *approximately* the same time of day in the order described below.

The Screening and Baseline visit windows are described below. The visit window for the additional PK visits on Day 8, 92, 120, 204, 232 and 316 is  $\pm 1$  Day. For all other visits, the window is  $\pm 3$  days. The window for the PK/PD assessments post dosing at 2 hours is +30 minutes. If the infusion rate is decreased (following an infusion site reaction) the PK/PD assessments should be collected at the time of infusion completion and flush (within a +30 minute window). Subjects are required to be observed for 1 hour after the administration of the investigational product is completed. The post-dosing vital sign will be taken upon completion of the investigational product administration during the 1-hour observation period.

At visits when both MRI-thigh and functional assessments are being conducted, these assessments should be conducted on *separate* days. Functional assessments should routinely be collected in the morning when the subject is rested and well-fed. The MRI-thigh should routinely be collected at approximately the same time of day throughout the study. Should subjects become non-ambulatory during the study, the 4SC, NSAA and 6MWT will not continue to be collected.

If a stool sample is unable to be collected during the screening visit, a collection kit and mailing supplies will be sent home and the caregiver will be responsible for collection and mailing the sample back to the site. For all other visits, a stool sample will be collected at home within approximately 1 week prior to the scheduled visit. Note that the collection may fall outside of the visit window.

For subjects who may be sexual mature at the onset of the study (as assessed during the baseline visit) or reach sexual maturity during the trial, as indicated by a Tanner Stage V rating, the Tanner Stage, testicular volume, hormone and X-ray (hand and wrist) will no longer be required to be collected during the study to assess for signs of precocious puberty.

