**6.6. Visits 6, 12, 18, 23, 27, 31 (Days 57, 169, 281, 393, 505, 617)**

This visit may be completed on the same day if logistics are permissive.

- **Fecal occult blood:** Fecal sample is to be collected at home within approximately 1 week prior to scheduled visit.
- **C-SSRS:** Children's Since Last Visit (Version 6/23/10).
- **PODCI Questionnaire.**

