**APPENDICES**

**Appendix 1. DATA DERIVATION DETAILS**

**Appendix 1.1. Definition and Use of Visit Windows in Reporting**

All windowing assignments will be reviewed by the study including any windowed visit with multiple observations more than 4 study days apart will be reviewed. Also any visits with no data will also be reviewed. Study windows may be adjusted to reflect appropriate data collection particular for the PK visits at weeks 2, 14, 18, 30, 34, and 46. The windowing definitions are included in Table 4. All windowing assignments are based on the relative study day. Relative study day 1 is always the first day of dosing.

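### SAP Table 4 closes the Week 37 window on Day 257, ten days before its own pattern gives (Day 267), so a permitted late Week 37 visit is assigned by default to Week 41

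*Protocol*

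**What the plan says.** The schedule comes from the Protocol. Section 6.5 lists "Visits 5, 11, 17, 22, 26, 30 (Days 29, 141, 253, 365, 477, 589", which puts Visit 17 (Week 37) on Day 253. Section 6.6 lists "Visits 6, 12, 18, 23, 27, 31 (Days 57, 169, 281, 393, 505, 617", which puts Visit 18 (Week 41) on Day 281.

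Section 6 of the Protocol sets the ordinary tolerance ("For all other visits, the window is" ±3 days). The text below the Period 2 dosing table in Section 5 covers a dosing visit that misses that tolerance: "attempts should be made to bring the subject back for dosing as soon as possible", with the limit that "dosing must not occur within 2 weeks prior to the next scheduled dose".

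The reporting windows are in SAP Table 4 (Appendix 1.1). Week 37 is given as Days 236 to 257 and Week 41 as Days 258 to 295. Appendix 1.1 states that "All windowing assignments are based on the relative study day". It also provides for review: "any windowed visit with multiple observations more than 4 study days apart will be reviewed", visits without data are reviewed as well, and windows may be adjusted.

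**The concern.** Week 37 is the one row of SAP Table 4 that does not follow the table's own pattern. A Week 37 visit held five or more days late drops into the Week 41 window, although the same delay at the corresponding visits of the two earlier dose blocks (Weeks 5 and 21) stays in its own window. Such a boy then has nothing under Week 37 and two visits under Week 41.

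Visit 17 carries pre-dose and end-of-infusion PK and GDF-8 samples, immunogenicity, iron indices, safety laboratory tests and vital signs. Its pre-dose PK sample is the trough after the first planned 40 mg/kg dose. By-visit summaries of these data would be short of a Week 37 record and would face a choice between two records at Week 41.

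**Working it through.** **Inputs.** Nominal days are from Protocol Sections 6.4 to 6.10 and windows are from SAP Table 4.

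**1. The pattern.** From Week 5 on, 18 windows are followed by a scheduled visit 28 days later with no PK-only visit between: Weeks 5, 9, 21, 25, 37, 41, 49, and every four weeks from 53 to 93. For each, take the last day of the window minus the nominal day. The result is +14, the midpoint of the 28-day gap, in 17 of the 18. The exception is Week 37: 257 − 253 = +4.

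**2. Week 37 and Week 41 beside their counterparts.**

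| Visit | Nominal day | Window | Opens | Closes | Length |
|---|---|---|---|---|---|
| Week 5 | 29 | 10–43 | −19 | +14 | 34 |
| Week 21 | 141 | 124–155 | −17 | +14 | 32 |
| Week 37 | 253 | 236–257 | −17 | **+4** | **22** |
| Week 9 | 57 | 44–71 | −13 | +14 | 28 |
| Week 25 | 169 | 156–183 | −13 | +14 | 28 |
| Week 41 | 281 | 258–295 | **−23** | +14 | **38** |

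**3. What the pattern gives.** (253 + 281) / 2 = Day 267, and 267 − 257 = 10 days. Week 37 then runs 236 to 267 (32 days) and Week 41 runs 268 to 295 (28 days), the same lengths as Weeks 21 and 25.

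**4. Could another rule give 257?** Windows that end just before a PK-only visit close at +3, which would give Day 256. The PK-only visits are on Days 8, 92, 120, 204, 232 and 316 (Protocol Section 6.4), and none lies between Days 253 and 281. Neither rule yields 257. The two rows meet without a gap (257, then 258), so a fault in reading the PDF is unlikely.

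**5. Which late visits are permitted?** The late-dosing limit is 281 − 14 = Day 267. Days 258 to 266 (5 to 13 days late) are 15 to 23 days before the next dose, so they are clearly allowed. Day 267 is exactly two weeks before it and depends on how the limit is read.

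**6. Which visit is nearer?** Day 258 is 5 days from Day 253 and 23 from Day 281. Day 266 is 13 and 15 days away. Day 267 is 14 from each. So every day from 258 to 266 is nearer to Week 37 but is assigned to Week 41.

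**The case against.** Table 4 gives only a default. Appendix 1.1 has all assignments reviewed, and a late Week 37 visit would normally trip both named checks. Week 37 would be empty. If Week 41 is held within Day 281 ± 3 (Days 278 to 284), the two visits in its window would be 278 − 266 = 12 to 284 − 258 = 26 days apart, well beyond the four-day trigger. This stands as a reason to expect detection. It does not say what happens next, because no reassignment rule is written.

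The SAP also has a filter for off-schedule samples. Section 6.3.1.2 sets PK concentrations to missing in summary tables and median plots where the sampling-time deviation is of enough concern, and Section 6.3.2.1 does the same for GDF-8. Some of the affected samples may therefore drop out of those summaries under either window. This also stands.

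The Table 4 column is labelled as an efficacy window, and no functional test is scheduled at Week 37. One could argue that the boundary never operates there. That holds only in part: Appendix 1.1 bases every assignment on study day and discusses the PK visits, so the table is not plainly confined to efficacy data.

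Finally, the visits at issue already lie outside the ±3-day tolerance, and the documents give no rate for such delays.

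**Conclusion.** The boundary is wrong by the table's own pattern: Day 257 where the other 17 comparable windows imply Day 267. By default, a permitted Week 37 visit on Days 258 to 266 is assigned to Week 41. This assumes that the visit's assessments are collected with the late dose.

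The reach is small. It covers descriptive by-visit summaries that use these windows: PK and GDF-8 concentrations, immunogenicity, laboratory data and vital signs. Week 37 is not a parameter visit in SAP Table 1 or in the GDF-8 table of SAP Section 3.3.2, and PK parameters are derived from actual sampling times (SAP Section 6.3.1.3.1). A late Week 37 visit brings no scheduled 4SC, and the Week 49 window (Days 320 to 351) follows the pattern, so the Week 49 4SC is untouched.

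A reader might infer that the misfiled sample seriously distorts the Week 41 trough. The documents do not support that. Assume one-compartment decline, on-schedule earlier doses of 5, 20 and 40 mg/kg, and a half-life of 14 to 18.5 days (Protocol Section 1.7 gives roughly 14 overall and 18 to 19 at higher doses). A delay of d days leaves 2^(−d/half-life) of the on-time Week 37 trough:

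- d = 5: 0.78 (14 days) or 0.83 (18.5 days)
- d = 14: 0.50 or 0.59

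The sample is thus already 17% to 50% below an on-time Week 37 trough because it was drawn late, and correct filing leaves that unchanged. On the same assumptions an on-time Week 37 trough is 88% to 90% of an on-time Week 41 trough, so misfiling itself accounts for only about 10% to 12%.

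Nor do the documents support a count of affected boys, or a claim that a misassigned record will certainly reach the final tables.

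**What to change.** In SAP Table 4, change Week 37 to Days 236 to 267 and Week 41 to Days 268 to 295, and update the windowing program. If the Day 257 boundary is intended, say why Week 37 differs. The cost is two numbers and one program edit, with no change to the Protocol, the visit schedule or any dosing rule.

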**Prior to dosing, the following procedures will be completed:**

**Clinical laboratory sample collection:**

- **Fasting blood collection:** serum ferritin, serum iron, TIBC and % transferrin saturation.
- **Blood sample** for Biomarker: Liver.
- **Blood sample** for hematology, chemistry, GGT, GLDH, PT, aPTT, creatine kinase and amylase.
- **Blood sample** for immunogenicity.
- **Urine** for urinalysis.
- **Blood sample** for PK.
- **Blood sample** for PD.
- **Weight:** Weight must be collected at each visit prior to dosing.
- **Physical Examination,** including nose and throat mucosal exam.
- **Vital signs:** Supine blood pressure, pulse rate, respiratory rate, and oral temperature.

**Dosing**

- **Investigational product administration.**

**After dosing, the following procedures will be completed:**

- **Vital signs:** Supine blood pressure, pulse rate, respiratory rate, and oral temperature.
- **Blood sample for PK:** Collected following the completion of infusion and flush (hour 2).
- **Blood sample for PD:** Collected following the completion of infusion and flush (hour 2).

- **Infusion site reaction monitoring.**
- **AE monitoring.**
- **Concomitant medication monitoring.**
- **Wellness phone check:** Approximately 1 week following each dosing visit, the site will call caregiver to verify if there are any AEs that have emerged since dosing.

**6.6. Visits 6, 12, 18, 23, 27, 31 (Days 57, 169, 281, 393, 505, 617)**

This visit may be completed on the same day if logistics are permissive.

- **Fecal occult blood:** Fecal sample is to be collected at home within approximately 1 week prior to scheduled visit.
- **C-SSRS:** Children's Since Last Visit (Version 6/23/10).
- **PODCI Questionnaire.**

**Prior to dosing, the following procedures will be completed:**

**Clinical laboratory testing:**

- **Fasting blood collection:** serum ferritin, serum iron, TIBC and % transferrin saturation.
- **Blood for Biomarker:** Liver.
- **Blood sample** for hematology, chemistry, GGT, GLDH, PT, aPTT, creatine kinase and amylase.
- **Blood sample** for immunogenicity.
- **Urine sample** for urinalysis.
- **Blood sample** for PK.
- **Blood sample** for PD.
- **Weight:** Weight must be collected at each visit prior to dosing.
- **Functional Assessments:** Must be conducted in the following order: FVC, 4SC, NSAA, ROM, strength assessment, PUL, 6MWT.
- **Physical Examination,** including nose and throat mucosal exam.
- **Vital signs:** Supine blood pressure, pulse rate, respiratory rate, and oral temperature.

## **Dosing**

- **Investigational product administration.**

### **After dosing, the following procedures will be completed:**

- **Vital signs:** Supine blood pressure, pulse rate, respiratory rate, and oral temperature.
- **Blood sample** for PK: Collected following the completion of infusion and flush (hour 2).
- **Blood sample** for PD: Collected following the completion of infusion and flush (hour 2).
- **Infusion site reaction monitoring.**
- **AE monitoring.**
- **Concomitant medication monitoring.**
- **Wellness phone check:** Approximately 1 week following each dosing visit, the site will call caregiver to verify if there are any AEs that have emerged since dosing.

### **6.7. Visits 7, 13, 19, 24, 28, 32 (Days 85, 197, 309, 421, 533, 645)**

- **Fecal occult blood:** Fecal sample is to be collected at home within approximately 1 week prior to scheduled visit.
- **C-SSRS:** Children's Since Last Visit (Version 6/23/10).

#### **Imaging assessments:**

- **MRI:** liver (Is able to be conducted at any time during the visit). If the E-DMC determines that the liver MRI monitoring is able to be reduced, it will then only be conducted at Visit 19 and 32 (Days 309 and 645).

### **Prior to dosing, the following procedures will be completed:**

#### **Clinical laboratory testing:**

- **Fasting blood collection:** serum ferritin, serum iron, TIBC, % transferrin saturation.
- **Blood sample** for Biomarker: Liver.
- **Blood sample** for hematology, chemistry, GGT, GLDH, PT, aPTT creatine kinase and amylase.

- **Blood sample** for immunogenicity.
- **Urine sample** for urinalysis.
- **Blood sample** for PK.
- **Blood sample** for PD.
- **Weight:** Weight must be collected at each visit prior to dosing.
- **Vital signs:** Supine blood pressure, pulse rate, respiratory rate, and oral temperature.
- **Physical Examination,** including nose and throat mucosal exam.

### **Dosing**

- **Investigational product administration.**

### **After dosing, the following procedures will be completed:**

- **Vital signs:** Supine blood pressure, pulse rate, respiratory rate, and oral temperature.
- **Blood sample** for PK: Collected following the completion of infusion and flush (hour 2).
- **Blood sample** for PD: Collected following completion of infusion and flush (hour 2).
- **Infusion site reaction monitoring.**
- **AE monitoring.**
- **Concomitant medication monitoring.**
- **Wellness phone check:** Approximately 1 week following each dosing visit, the site will call caregiver to verify if there are any AEs that have emerged since dosing.

### **6.8. Visits 9, 15, 21, 25, 29 (Days 113, 225, 337, 449, 561)**

A two day visit will be required to complete assessments at this visit. MRI-thigh and functional assessments should be collected on separate days. Functional assessments should routinely be collected in the morning when the subject is rested and well fed. The MRI-thigh should routinely be collected at approximately the same time of day throughout the study.

- **Fecal occult blood:** Fecal sample is to be collected at home within approximately 1 week prior to scheduled visit.
- **C-SSRS:** Children's Since Last Visit (Version 6/23/10).

- **PODCI** questionnaire.

**Imaging assessments:**

- **DXA:** whole body (following 2 hour fast).
- **DXA:** spine Visit 21 (Day 337) only.
- **MRI:** thigh Visit 9, 15, 21 (Days 113, 225 and 337) only.
- **X-ray:** non-dominant hand and wrist.
- **Cardiac MRI** (with or without gadolinium) or **Echocardiogram** Visit 21 (Day 337) only. The modality used to monitor LVEF should be consistent throughout the study for each subject, if cardiac MRI with gadolinium is used, the imaging may only be performed following all other imaging at the study visit.
- **Triplicate ECG.**
- **Tanner Stage** and **testicular volume.**
- **Functional assessments:** Must be conducted in the following order: FVC, 4SC, NSAA, ROM, strength assessment, PUL, 6MWT.

**Prior to dosing, the following procedures will be completed:**

**Clinical laboratory testing:**

- **Fasting blood collection:** serum ferritin, serum iron, TIBC and % transferrin saturation.
- **Blood sample** for hormones (LH, FSH, T4, TSH, androstenedione, testosterone). Blood collection for hormones should be done in the morning.
- **Fasting blood** collection for Biomarker: Group 2.
- **Blood sample** for Biomarker: Group 3 at Visit 21 (Day 337) only.
- **Blood sample** Biomarker: Liver.
- **Blood sample** for hematology, chemistry, GGT, GLDH, PT, aPTT, creatine kinase, amylase and cardiac Troponin I.
- **Blood sample** for immunogenicity.
- **Urine sample** for urinalysis.

- **Blood sample** for PK.
- **Blood sample** for PD.
- **Weight:** Weight must be collected at each visit prior to dosing.
- **Height:** Height should be measured in the morning.
- **Physical Examination**, including nose and throat mucosal exam.
- **Vital signs:** Supine blood pressure, pulse rate, respiratory rate, and oral temperature.

